7.6 Safety Event Follow up and Sponsor Reporting

AEs and SAEs directly related to study procedures will be followed until resolution even if this extends beyond the study-reporting period. Resolution of an AE is defined as the return to pretreatment status or stabilization of the condition with the expectation that it will remain chronic. If the event resolves during the study or follow-up period, a resolution date should be documented on the eCRF.

AEs directly related to study procedures and safety ESIs (that are not defined as an SAE) will be reported in the data system within 7 days of identification/site awareness.

SAEs, SUSARs, and safety ESIs that are associated with any of the criteria that define the event as an SAE will be reported in the data system within 24 hours of identification/site awareness. Upon entry in the Electronic Data Capture (EDC) system, these events will generate an automatic email notification to the DCC, DCC MM, and the sponsor. The investigator/delegate (defined as a clinician licensed to make a diagnosis) must document their assessment of severity and causality in the participant records in a timely manner and submit safety reports as required by their IRB/REB/IEC.

The DCC MM will review all events at the time they are reported. Any event that requires expedited reporting based on federal regulations (21CFR 312.32) will be forwarded to the IND sponsor or the in-country designee. The IND sponsor or its representative will submit expedited safety reports (e.g., IND safety reports) to the regulatory agencies as necessary.

For non-US sites, the sponsor investigator's in-country designee must comply with all local regulatory requirements related to submitting reportable events to a regulatory authority and IEC. Documentation of the submissions must be retained for each reported event (annual or expedited) and provided to the DCC. The sponsor-investigator (or designee) will inform the investigators of any SUSAR safety reports submitted to a regulatory authority.

7.6.1 Pregnancy

Contraception is allowed but will not be required for participants. Although not considered an AE, if a pregnancy occurs during the study, it must be reported immediately by the site. The participant will be allowed to continue in the study but will be withdrawn from study products,

given an appropriate referral, and followed until resolution of the pregnancy. At the time of study product discontinuation, the participant will be asked to complete an ECG and provide a PK blood sample and their parent(s)/legal guardian(s) will be asked to complete the ABC. No further procedures will be done. Participants will then be followed for safety for at least 5 (+ 2) days after the last study dose. The site must document that they have informed the Sponsor, advised the participant to obtain appropriate prenatal medical care, and referred the participant for such care.

The site may be required to inform parent(s)/legal guardian(s) about pregnancies according to local/state laws. In addition, per the consent, researchers will follow the participant for the duration of the pregnancy and to obtain information (via direct examination or medical record review) to determine whether the resulting fetus/newborn survived delivery or had any congenital abnormalities. If the fetus/newborn does not survive delivery or any congenital abnormalities are present, these must be reported as an SAE following the usual requirements for SAE reporting. Please note that if a pregnancy is reported, the participant's subsequent weight, vital sign, and laboratory data will not be included in analyses for these variables. If the pregnancy is terminated, elective or otherwise, within the first 12 weeks of the pregnancy, inclusion of the participant's subsequent weight/height, vital signs, and laboratory data in the analyses will be determined by the PTN study team.

7.7 Regulatory Reporting

Any event that requires expedited reporting based on federal regulations will be forwarded to the IND sponsor via reporting on the study specific eCRF. The IND sponsor or its representative as detailed in the Transfer of Regulatory Obligations (TORO) will submit expedited safety reports (e.g., IND safety reports) to the FDA and other regulatory agencies as necessary and will inform the investigators of such regulatory reports. Site investigators must submit safety reports as required by their IRB/REB/IEC. Documentation of the submission and receipt by the IRB/REB/IEC must be retained for each expedited safety report.

Any event that requires reporting to Regulatory Authorities (e.g., SUSARS) based on applicable national regulations will be forwarded to the IND sponsor in time to meet reporting requirements.

7.8 Data & Safety Oversight (Medical Monitor/Data Safety Monitoring Board)

The study will be monitored by the BPCA DSMB. The DSMB is chartered by NIH to support all research activities conducted under the PTN.

In addition, the study has designated a qualified and experienced physician not otherwise associated with this protocol to serve as the MM and review all SAEs at the time they are reported and/or updated. The MM may request additional information regarding a site reported SAE; the site PI is expected to provide requested information or materials to the MM in an expeditious manner to support the writing/submission of study safety reports. The MM will be available to study sites as needed. The study IND sponsor will also review all SAEs to determine regulatory reporting and will be available to sites as needed.

If safety concerns are identified, the MM may request a meeting of the DSMB to review safety data. The MM will also provide an initial report to the study PI/sponsor and an unbiased written report to the DSMB of the event per the DSMB charter/safety monitoring plan. At a minimum, the MM will comment on the outcomes of the SAE and the relationship of the SAE to the study product. The MM will also indicate whether they concur with the details of the report provided by the study site investigator. If no SAEs prompt review at an earlier time point, the DSMB will review AEs and SAEs per the DSMB charter.

The DSMB will convene and make recommendations on termination of the study based on review of safety reports and halting rules. The safety data will be compiled by the DCC. Based on the recommendations of the DSMB, PTN, and NIH/NICHD, the IND sponsor will make a decision to terminate or continue the study.

Ad Hoc Meetings of the DSMB: The DSMB may convene an *ad hoc* meeting to discuss any issue of data and safety raised by the site investigator, the MM, the IND sponsor, NICHD, or a member of the DSMB. At the discretion of the investigators, the IND sponsor, NICHD, and DSMB members, a non-serious AE that is associated with the product or procedures may be considered as a trigger for an *ad hoc* DSMB meeting to assess the safety of the product, without resulting in halting the enrollment of the trial.

8 STUDY HALTING/TERMINATION

8.1 Study or Site Halting Criteria/Termination Criteria

This study may be terminated at any time by NICHD, the IND sponsor, or via recommendations by the DSMB to NICHD.

Reasons for termination include, but are not limited to, if in their judgment, there are no further benefits to be achieved from the study or if the treatment presents an unreasonable and significant risk to participants. If the study is terminated, notifications will be made to the regulatory authorities (e.g., FDA), investigators, IRBs/REBs, or study participants, in accordance with all applicable regulations governing the study and site/investigator.

A participating site/investigator may be terminated at any time by the sponsor, regulatory authority or by a ruling of the IRB/REB. Possible reasons for termination of the study at a site include, but are not limited to:

- Non-compliance with signed agreements, statements, or undertakings
- Safety concerns
- Inaccurate or incomplete data collection
- Falsification of records
- Failure to adhere to the protocol

If the site/investigator is terminated, notifications will be made to regulatory authorities, IRBs/REBs, or other concerned parties in accordance with the applicable regulations governing the study and site/investigator.

8.2 Halting Rules

No halting rules are planned.

9 CLINICAL MONITORING

Clinical site monitoring is conducted to ensure that the rights and well-being of study participants are protected, that the reported study data are attributable, legible, contemporaneous, original, accurate, complete (ALCOA-C), and that the conduct of the study is in compliance with the currently approved protocol/amendment(s), with ICH GCP [E6 (R2)], and with applicable regulatory requirement(s), including 21 CFR 312 Subpart D Responsibilities of Sponsors and Investigators.

The PTN PI or the DCC as detailed in the TORO, or their designee will conduct site-monitoring visits. Site visits will be made at standard intervals as defined by the clinical site monitoring plan appendix but may be made more frequently as directed by the DCC, IND sponsor, and/or NICHD. Monitoring visits will include, but are not limited to, review of regulatory files, accountability records, data collection forms, informed consent forms, medical and laboratory reports, and protocol compliance. Study monitors will meet with investigators to discuss any problems and actions to be taken and document visit findings and discussions.

The study-specific clinical site monitoring plan appendix will supplement the BPCA project-wide clinical monitoring plan based on protocol risk assessments.

10 STATISTICAL CONSIDERATIONS

Efficacy, PK, safety, and exploratory analyses will be conducted. Participant demographics will be summarized. In addition, the number of participants enrolled, completed or discontinued early from study, and the reasons for discontinuation will also be summarized.

Descriptive statistics, such as the number of observations, mean, median, 95% confidence interval, standard deviation (SD), standard error, minimum, and maximum, will be considered for continuous variables (e.g., age, weight, etc.). Other descriptive statistics, such as counts, proportions, and/or percentages, will be presented to summarize discrete variables (e.g., sex, race, etc.).

10.1 Study Hypotheses

Improvement in the ABC-H subscale from baseline over an 8-week trial will be greater with GIR compared to placebo in children with DS.

10.2 Study Endpoints

10.2.1 Primary Endpoint

Primary Endpoint:

- Change from baseline to Week 8 of the parent-rated ABC-H subscale score

The following will serve as the secondary efficacy endpoints:

- Change from baseline to Week 4 of the parent-rated ABC-H subscale score
- Proportion of participants with a CGI-I score of 2 or better at Week 4 and Week 8

10.2.2 Secondary Endpoints

The following safety endpoints will be collected throughout the Week-8 treatment period of the study:

- Incidence of SAEs
- Incidence of safety ESIs
- Incidence of AEs

10.2.3 Exploratory Endpoints

The following PK endpoints will be estimated at Week 4 and Week 8:

- Guanfacine HCl plasma concentrations ($C_{\max,ss}$ and $C_{\min,ss}$)
- Time at peak concentration ($T_{\max,ss}$)
- Apparent area under the concentration versus time curve at steady state (AUC_{ss}/F)
- Apparent clearance (CL_{ss}/F)
- Volume of distribution (V/F)
- Half-life ($t_{1/2}$)

The following will be used to characterize the exposure-response relationship of GIR for the treatment of hyperactivity/impulsivity, inattention, and sleep quality in children with DS at Week 4 and Week 8:

- Guanfacine HCl plasma concentrations ($C_{\max,ss}$ and $C_{\min,ss}$)
- Area under the concentration time curve (AUC_{ss})
- ABC-H subscale score
- CGI-I

- Epworth Sleepiness Scale for Children and Adolescents (ESS-CHAD)
- Child's Sleep Habits Questionnaire (CSHQ)

10.3 Analysis Population

10.3.1 Intention-to-Treat (ITT) Population

The ITT population consists of all randomized participants.

10.3.2 Per-Protocol Population

Analyses may be conducted for a per-protocol population that only considers participants who are at least 70% compliant in taking study product for the 8-week study period and who receive the correct randomized treatment.

10.3.3 PK Population

All participants enrolled with at least 1 evaluable PK sample will be included in the PK analysis.

10.3.4 Safety Population

The safety population includes all participants who consume at least one dose of study product. This population may be identical to the ITT population.

10.3.5 Efficacy Population

The efficacy population includes all ITT participants with at least 1 follow-up efficacy measurement at Week 4 or Week 8. This population may be identical to the ITT population.

10.4 Analysis Plan

Descriptive statistics, such as number of observations, mean, median, SD, standard error, minimum, and maximum, will be presented for continuous variables (e.g., age, weight, etc.). Other descriptive statistics, such as counts, proportions, and/or percentages, will be presented to summarize discrete variables (e.g., race, sex, etc.). All descriptive analyses will be presented by appropriate treatment group and overall. A 95% confidence level will be used for confidence intervals. A detailed description of statistical methods and secondary analyses will be prepared and presented in the statistical analysis plan prior to data lock for final analyses.

10.4.1 Primary Analysis

The primary objective of this study is to determine GIR efficacy for the treatment of hyperactivity, inattention, and impulsivity in children with DS using the ABC-H scale. This objective will be evaluated using the endpoint of change from baseline to Week 8 of the ABC-H subscale score. The ABC-H subscale is a continuous scale with a minimum score of zero to a maximum score of 48, so the primary analysis will be conducted assuming a normal distribution. A mixed effect model analysis will be conducted to compare the change in ABC-H subscale score from baseline. Analysis will be conducted in SAS statistical analysis software using a PROC MIXED procedure. Fixed effects in the model will include indicator for the treatment assignment (GIR vs. placebo), baseline ABC-H score, and assessment week. To account for the correlation of longitudinal scores collected at baseline, Week 4, and Week 8, a participant level random intercept will be included in the model. The primary endpoint (effect size, p-value, and 95% confidence interval) of difference in the change from baseline to Week 8 of the ABC-H subscale will be evaluated using a contrast statement in the model. Additional analysis to evaluate impact of other covariates, including age, sex, weight, comorbid diagnosis of ASD, use of alternative agent(s) to treat ADHD, site, cumulative dose, demographics, may also be conducted. A sensitivity analysis may also be performed to determine how the missing data mechanism affects the primary outcome results.

Secondary efficacy outcome measures: GIR effectiveness for the treatment of hyperactivity, impulsivity, and inattention in children with DS will also be assessed using change from baseline to Week 4 of the ABC-H subscale score and with the CGI-I specific to hyperactivity, inattention, and impulsivity behaviors. The change from baseline to Week 4 of the ABC-H subscale score will be analyzed using the mixed effects model described above. The CGI-I is measured on a 7 point Likert scale from “very much improved” to “very much worse.” The proportion of participants with a CGI-I of “1-very much improved” or “2-much improved” will be analyzed as a dichotomous outcome. These dichotomized outcomes will be analyzed using a generalized linear mixed model with binary distribution and logit link. All mixed models for secondary efficacy endpoints will include covariates identified above for the analysis of primary efficacy endpoint.

In addition to the modelling analysis to obtain the effect size, p-value, and 95% confidence intervals, summary statistics for continuous, nominal, and ordinal outcomes at each of the visits will be presented by treatment group (GIR vs. placebo) and overall.

Table 4. Distribution of CGI-I for Secondary Efficacy Outcome Measure

Scale	Distribution of Outcome Scale	Outcome Values
The Clinical Global Impressions Scale - Improvement (CGI-I)	Ordinal	0 = not assessed 1 = very much improved 2 = much improved 3 = minimally improved 4 = no change 5 = minimally worse 6 = much worse 7 = very much worse

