6.13 Dosage and Study Drug Information

6.13.1 Dose Timing

Dose escalation

Study product will be administered once daily (q.h.s.) during the first 5 (+ 2) days of study product administration and then twice daily thereafter. Twice daily doses may be administered in uneven BID dosing; for example, a total daily dose of 2.0 mg can be divided into 0.5 mg in the morning and 1.5 mg in the evening, at the discretion of the clinical provider. Dose escalation will occur based on the details in **Table 3** with the highest dose being dose level 6. Participants in both the GIR and placebo arms will be evaluated for potential dose escalation every 5 (+ 2) days via a Dose Escalation Assessment (via telephone during Weeks 1-3 and 5-7 or in-person at Week 4) described in Section **6.8**. Parent/legal guardian will be asked to measure HR and BP prior to each dose escalation assessment. If there is a safety concern during the weekly Dose Escalation Assessments (via telephone during Weeks 1-3 and 5-7 or in-person at Week 4) as stated in Section **6.8**, or for any other reason, the sites will be instructed on the following:

1. Hold at current dose/schedule for 5 (+ 2) days (or advance directly to step #3 or step #5 below, if deemed appropriate by the clinical provider)

2. Reassess at next dose-escalation assessment
3. If sedation is a significant concern, divide the total daily dose and give higher dose proportion at bedtime (q.h.s); example: 2 mg totally daily dose split as 0.5 mg in the morning and 1.5 mg q.h.s and
4. Reassess at next dose-escalation assessment
5. If safety concern remains, reduce total daily dose to the lower dose previously tolerated

Table 3. Dose Escalation Plan*

Dose Level	Total daily dose for weight \geq 25 kg (mg)
1	0.5
2	1.0
3	1.5
4	2.0
5	2.5
6	3.0

* Parent/legal guardian will be asked to measure HR and BP prior to each dose escalation assessment.

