A population ER analysis may be performed to characterize the PK/ER relationship between GIR exposure (e.g., $C_{max,ss}$, AUC_{ss}) and selected safety and efficacy endpoints (e.g., hyperactivity, impulsivity, inattention, or sleep quality in children is observed). The sleep quality will be assessed via the CSHQ and ESS-CHAD (see **Table 5**). These are continuous outcomes that will be analyzed similar to the primary outcome using a mixed effects model. Epworth Sleepiness Scale for Children and Adolescents (ESS-CHAD) will also be analyzed as a dichotomous outcome; scores ≥ 10 are “sleepy” and scores <10 are “normal” using a generalized linear mixed model with binary distribution and logit link.

Table 5. Distribution of Scales for Exploratory Outcome Sleep Quality Measures (CSHQ and ESS-CHAD)

Scale	Distribution of Outcome Scale	Outcome Values
Child's Sleep Habits Questionnaire (CSHQ, Abbreviated Version)	Continuous	Minimum Total Score: 33 Maximum Total Score: 99
Epworth Sleepiness Scale for Children and Adolescents (ESS-CHAD)	Continuous	Minimum Total Score: 0 Maximum Total Score: 24

Different PK/ER models, including logistic regression model for binary safety outcomes, efficacy outcomes, and linear, log-linear, and E_{max} models for continuous safety/efficacy outcomes, may be explored. The ER model development, evaluation, and validation will be similar to that described above for population PK model.

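### The primary mixed model lists no treatment-by-week term, so its Week 8 contrast cannot isolate Week 8 and the Week 4 secondary result is the same number

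*Combined protocol and SAP*

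**What the plan says.** Sections 3 and 10.2.1 define the primary endpoint as change in parent-rated ABC-H from baseline to Week 8. Change to Week 4 is a separate secondary endpoint. Section 10.6 bases the sample size on a Week 8 difference.

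Section 10.4.1 gives the model:

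- Fixed effects: "Fixed effects in the model will include indicator for the treatment assignment (GIR vs. placebo), baseline ABC-H score, and assessment week".
- Random effect: "To account for the correlation of longitudinal scores collected at baseline, Week 4, and Week 8, a participant level random intercept will be included".
- Primary result: the "difference in the change from baseline to Week 8 of the ABC-H subscale will be evaluated using a contrast statement in the model".
- Week 4 secondary endpoint: "The change from baseline to Week 4 of the ABC-H subscale score will be analyzed using the mixed effects model described above".

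Other analyses reuse the structure. For the secondary efficacy models, "All mixed models for secondary efficacy endpoints will include covariates identified above for the analysis of primary efficacy endpoint"; one of those endpoints is the "Proportion of participants with a CGI-I score of 2 or better at Week 4 and Week 8". For the sleep scales, section 10.4.3 says "These are continuous outcomes that will be analyzed similar to the primary outcome using a mixed effects model".

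No treatment-by-week or treatment-by-visit term is named in any section. Section 10.4 defers detailed methods to an analysis plan to be written before data lock; the document in hand contains no such detail.

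**The concern.** A model with treatment and week as main effects assumes that the GIR–placebo difference is the same at Week 4 and Week 8. No contrast statement can then recover a difference specific to Week 8, because the model has no parameter for it. The primary estimate answers a different question from the primary endpoint, and the primary and Week 4 results are one result reported twice.

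Equal effects at the two visits cannot be presumed. Section 4.4 runs dose escalation to day 49, and section 6.13.1 has both arms "evaluated for potential dose escalation every 5 (+ 2) days". Some children may still be below their eventual dose at the Week 4 visit. The document does not give the size or direction of any difference between the Week 4 and Week 8 effects.

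There is a second ambiguity in the same paragraph. Baseline ABC-H is named both as a covariate and as one of the correlated longitudinal scores, so it is unclear whether baseline is also a response row.

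**Working it through.** **1. The plan's own figure (section 10.6).** Inputs: Week 8 means 26 and 20.6, SD 6, 48 evaluable, two-sided alpha 0.05, equal-variance t-test; 2:1 allocation from section 4.2.1, hence 32 vs 16.

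- Difference = 26 − 20.6 = 5.4; d = 5.4/6 = 0.90.
- Standard error = 6 × √(1/32 + 1/16) = 1.84.
- Noncentral-t power, 46 df: 82.1%. This agrees with the stated figure of more than 80%.
- 48/(1 − 0.20) = 60, also as stated.

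**2. What the listed model estimates.** Let D4 and D8 be the true differences at Weeks 4 and 8. With change scores at both visits, complete data and a random intercept (equal variances, one correlation), the single treatment coefficient estimates (D4 + D8)/2. Both the Week 8 and the Week 4 contrast return this coefficient.

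Write D4 = f × D8. The target is 5.4 × (1 + f)/2. The SD of a participant's two-visit mean is 6 × √((1 + ρ)/2), where ρ is the correlation of the two change scores.

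Assumptions not in the document: f; ρ between 0.5 and 0.8; SD 6 at Week 4 as well as Week 8. The baseline covariate is ignored on both sides of the comparison.

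| f | Target of listed model | Power, ρ = 0.8 | Power, ρ = 0.5 |
|---|---|---|---|
| 0.50 | 4.05 | 62% | 70% |
| 0.75 | 4.73 | 76% | 83% |
| 0.85 | 5.00 | 80% | 87% |
| 1.00 | 5.40 | 86% | 91% |

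The listed model matches the planned 82% when (1 + f)/2 = √((1 + ρ)/2), that is f = √(2(1 + ρ)) − 1. This gives f = 0.73, 0.79, 0.84 and 0.90 at ρ = 0.5, 0.6, 0.7 and 0.8. Below those values the listed model has less power than planned, above them more.

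**3. Check by simulation.** Random-intercept fits to 200 simulated trials at each f, with ρ = 0.65:

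| f | Mean estimate, listed model | Mean Week 8 estimate, treatment × week added | Significant, listed | Significant, with interaction |
|---|---|---|---|---|
| 0.50 | 4.05 | 5.36 | 65% | 85% |
| 0.75 | 4.72 | 5.40 | 78% | 82% |
| 1.00 | 5.38 | 5.38 | 89% | 83% |

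**4. Missing Week 8 scores.** If a fraction p of participants have Week 8 data and all have Week 4 data, the weight on Week 8 is (1 − ρ)/[1 + (1 − ρ²)/p + ρ² − 2ρ]. At ρ = 0.5 and p = 0.8 (20% missing, borrowing the plan's dropout figure) this is 0.5/1.1875 = 0.42. With f = 0.5 the target becomes 2.70 + 0.42 × 2.70 = 3.84, down from 4.05. Dropout pulls the result further toward Week 4.

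**5. If baseline is a response row.** With a zero change at baseline kept as a row, the target is (0 + D4 + D8)/3: 2.70, 3.15 and 3.60 points at f = 0.5, 0.75 and 1. With raw scores at three visits as the response, the treatment difference is the same at every visit, so a contrast of differences in change is τ − τ = 0 by construction.

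**6. Dose timing.** Level k starts on Day 1 + 5(k − 1) at the fastest steps and Day 1 + 7(k − 1) at the slowest regular steps. Level 6 is therefore first reachable between Day 26 and Day 36. The Week 4 visit falls on Days 22–28 (± 3).

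**The case against.** The strongest reply is that the interaction was intended. The paragraph says what the fixed effects will include, which need not be exhaustive; a Week 8 contrast has little purpose in a main-effects model; and section 10.4 promises a fuller analysis plan. That is probably right about intent. It does not repair the text. The paragraph names its fixed effects, a programmer following it would omit the term, and adding the term after unmasking would look like a data-driven change to the primary model. If the list is not exhaustive, the primary model is not fully prespecified.

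Several narrower points stand:

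- The averaging result depends on response rows at Weeks 4 and 8 only. Step 5 shows that the other readings do not give the Week 8 difference either.
- Power loss is not certain. Above the break-even f the listed model has more power than planned, and if there is no effect at either visit its test remains valid. It is not a test of Week 8 alone, however: an effect at Week 4 with none at Week 8 would still give a nonzero target, D4/2.
- The Week 4 SD, f and ρ are assumptions.
- The dose schedule permits different effects but does not show them. Level 6 can be reached on Day 26, inside the Week 4 window, and section 6.8 withholds escalation once CGI-I is 1 or 2.
- The extension to CGI-I and the sleep scales is less firm. Section 10.4.1 does not say that CGI-I at Weeks 4 and 8 share one model, CGI-I is collected weekly, and the sleep analyses are exploratory.

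**Conclusion.** The concern holds and must be fixed. Followed literally, section 10.4.1 produces a primary estimate that is not the Week 8 difference defined in section 10.2.1 and powered in section 10.6, and it gives the Week 4 secondary endpoint the same estimate, interval and p-value. These conclusions follow from the listed terms and need no assumption about f or ρ; the primary estimate is harmless only if the two visit effects are equal.

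The size is conditional. At f = 0.5 the target falls from 5.4 to 4.05 points and power from 82% to 62–70%; the listed model loses power relative to plan only when f is below about 0.73 (ρ = 0.5) to 0.90 (ρ = 0.8). The exact equal weighting requires complete data. The double role of baseline is a separate ambiguity that could make the result worse.

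**What to change.** Replace the model description in section 10.4.1 with wording such as:

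> Response rows are change from baseline at Week 4 and Week 8; baseline ABC-H is a covariate only. Fixed effects are treatment, assessment week (categorical), treatment × week and baseline ABC-H, with a participant random intercept. The primary estimate is the GIR–placebo difference at Week 8. The Week 4 secondary estimate is the GIR–placebo difference at Week 4 from the same model.

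Add treatment × week to the CGI-I logistic mixed model and state which weeks are its response rows. Add it to the sleep-scale models wherever visit-specific effects are reported. Carry the same wording into the analysis plan before data lock. No other change to the model is needed for this defect.

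Sample size, visits and data collection do not change. The cost is precision if the effect really is the same at both visits: the Week 8 standard error is then 1.84 points instead of 1.74 (ρ = 0.8) or 1.59 (ρ = 0.5), which is 5–15% larger, and power is 82% instead of 86–91%. That 82% is the power section 10.6 already planned for.
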